	group, a more sufficient power of detection will be obtained by
	changing the randomization ratio. In this trial, it is assumed that the
	difference between the 2 mg group and the placebo group in the
	change in the CMAI total score from baseline to Week 10 is -5.35 ,
	and the standard deviation (calculated from the standard error of the
	difference between the 2 mg and placebo groups and the number of
	subjects at baseline) is 15.06 on the basis of the results of Trial 331-
	12-283. By setting the number of subjects in the 2 mg group, 1 mg
	group, and placebo group as 148, 111, and 148, respectively
	(randomization ratio of 4:3:4), the power of detection is 86.1% for
	the comparison between the 2 mg group and the placebo group and is
	80.5% for the comparison between the 1 mg group and the placebo
	group in a test with a significance level of 5% (two sided).
	On the basis of the above considerations, the number of subjects will
	be set at 148 in the 2 mg group, 111 in the 1 mg group, and 148 in
	the placebo group (randomization ratio of 4:3:4).
Trial duration:	August 2018 to June 2023 (planned)
	The duration of participation in the trial by each subject will be up to
	20 weeks.

Table of Contents

Proto	col Synopsis	2
Table	of Contents	7
List o	f In-text Tables	13
List o	f In-text Figures	14
List o	f Appendices	15
List o	f Abbreviations and Definitions of Terms	16
1	Introduction	18
1.1	Background	18
1.2	Nonclinical Data	20
1.3	Clinical Data	21
1.3.1		
		21
1.3.1.1		21
1.3.1.2		23
1.3.1.3		25
1.4	Known and Potential Risks and Benefits	
2	Trial Rationale and Objectives	27
2.1	Trial Rationale	27
2.2	Rationale for CYP2D6 Genetic Testing and DNA Storage	
2.3	Rationale of Sample Storage for Biomarker Exploration	29
2.4	Trial Objectives	
3	Trial Design	
3.1	Type/Design of Trial	
3.2	Trial Treatments	32
3.2.1	Dosing and Regimen	32
3.2.2	Rationale for Dosing and Regimen	32
3.2.3	Rationale for Duration of Treatment	34
3.3	Trial Population	34
3.3.1	Number of Subjects and Trial Population	34
3.3.2	Subject Number Assignment	34
3.4	Eligibility Criteria	35

3.4.1	Informed Consent	35
3.4.2	Inclusion Criteria	36
3.4.3	Exclusion Criteria	38
3.5	Requirements for Caregivers	41
3.6	Endpoints	42
3.6.1	Primary Endpoint	42
3.6.2	Secondary Endpoints	42
3.6.3	Exploratory Endpoints	42
3.6.4	Safety Endpoints	42
3.6.5	Pharmacokinetic Endpoint	43
3.6.6	Pharmacogenomic Endpoint	43
3.6.7	Other Endpoints	43
3.7	Measures to Minimize/Avoid Bias	43
3.8	Trial Procedures	45

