2.1 Trial Rationale

It is considered that neurotransmitters such as serotonin, dopamine and noradrenaline are involved in agitation. Brexpiprazole, which regulates the serotonin-dopaminergic system, is expected to improve agitation in patients with dementia of the Alzheimer's type while suppressing expression of extrapyramidal symptoms.

Based on the results of the 2 overseas confirmatory trials in agitation associated with dementia of the Alzheimer's type (Trial 331-12-283 and Trial 331-12-284), and because

the PK of brexpiprazole is not affected by ethnicity, it is considered that brexpiprazole will also show efficacy in Japanese patients with agitation associated with dementia of the Alzheimer's type.

In the overall population of Trial 331-12-284, no statistically significant differences were noted in the flexible-dose brexpiprazole group compared with the placebo group, but the results of an additional analysis showed the efficacy of brexpiprazole in patients with aggression.

On the basis of these findings, a multicenter, placebo-controlled, randomized, doubleblind, parallel-group comparison trial to verify the superiority of brexpiprazole over placebo, evaluate the safety of brexpiprazole, and confirm an optimal dose in Japanese patients with aggression in agitation associated with dementia of the Alzheimer's type was planned. The doses of brexpiprazole were determined with reference to the data of the 2 overseas trials, and two doses were selected: a dose of 2 mg, which showed a statistically significant improvement compared with the placebo group in Trial 331-12-283 and might be an optimal dose in Japanese patients, and a dose of 1 mg to obtain the dose-response relationship in Japanese patients. Duration of treatment was set to 10 weeks.

Furthermore, on the basis of the report¹⁹ of the risk of death associated with atypical antipsychotics, criteria to exclude patients at high risk of cerebrovascular disorder, cardiac disorder, pneumonia, and other infections, which were the causes of death associated with atypical antipsychotics, were established to minimize the risk to subjects during the trial and an Independent Data Monitoring Committee (IDMC) was established to monitor safety during the trial, as measures to ensure subject safety.

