9.2.1 Adverse Events of Interest

Each AE of interest is defined in Appendix 4. Numbers and proportions of subjects with the following AEs of interest will be summarized by SOC and PT for each treatment group and for the overall brexpiprazole group.

- Extrapyramidal AEs
- Accident- and injury-related AEs
- Cerebrovascular AEs
- Cardiovascular AEs
- Glucose metabolism-related AEs
- Lipid metabolism-related AEs
- Body weight-related AEs
- Blood disorder-related AEs
- Hypersensitive symptom-related AEs
- Neuroleptic malignant syndrome-related AEs
- Orthostatic disorder-related AEs
- Prolactin increase-related AEs
- QT interval prolongation-related AEs
- Rhabdomyolysis
- Seizure-related AEs
- Oversedation-related AEs
- Suicide/suicide attempt-related AEs
- Venous thrombosis
- Pneumonia-related AEs

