Electric injury

Electric shock

Electrocution

Enophthalmos traumatic

Epidural haemorrhage

Epiphyseal fracture

Epiphyseal injury

Epiphysiolysis

External genitalia crushing

Extradural haematoma

Extrahepatic biliary tree injury

Eye abrasion

Eye contusion

Eye injury

Eye luxation

Eyeball avulsion

Eyelash injury

Eyelid contusion

Eyelid haematoma

Eyelid injury

Face crushing

Face injury

Facial bones fracture

Facial nerve injury due to birth trauma

Fall

Femoral neck fracture

Femoral nerve injury

Femur fracture

Fibula fracture

First degree chemical burn of skin

Flail chest

Foot fracture

Forearm fracture

Foreign body aspiration

Foreign body in eye

Foreign body in gastrointestinal tract

Foreign body in mouth

Foreign body in reproductive tract

Foreign body in respiratory tract

Foreign body in skin or subcutaneous tissue

Foreign body in throat

Foreign body in urogenital tract

Foreign body ingestion

Fourth degree chemical burn of skin

Fracture

Fracture displacement

Fracture of clavicle due to birth trauma

Fracture of penis

Fracture pain

Fractured coccyx

Fractured sacrum

Fractured skull depressed

Frostbite

Gallbladder injury

Gallbladder rupture

Gastrointestinal injury

Gastrointestinal organ contusion

Version: 1.0 Date: 01/06/2023

Genital contusion

Genital injury

Gingival injury

Glaucoma traumatic

Greenstick fracture

Gun shot wound

Haematuria traumatic

Haemothorax

Hand fracture

Hanging

Head crushing injury

Head injury

Heat cramps

Heat exhaustion

Heat stroke

Hepatic rupture

Hernia perforation

High-energy trauma

Hip fracture

Human bite

Humerus fracture

Hyperthermia

Hyphaema

Hypothermia

IIIrd nerve injury

IVth nerve injury

Ilium fracture

Impacted fracture

Implant site injury

Inguinal hernia perforation

Injury

Injury corneal

Injury of conjunctiva

Injury to brachial plexus due to birth trauma

Internal injury

Intervertebral disc injury

Intra-abdominal organ avulsion

Intra-abdominal vascular injury

Iris injury

Iris tear

Jaw fracture

Joint dislocation

Joint hyperextension

Joint injury

Keratorhexis

Keraunoparalysis

Kidney contusion

Kidney rupture

Laryngeal injury

Lens dislocation

Lenticular injury

Ligament injury

Ligament rupture

Ligament sprain

Limb crushing injury Limb fracture

Limb injury

Limb reattachment surgery

Limb traumatic amputation

Lip injury

Lisfranc fracture

Liver contusion

Liver injury

Loose body removal

Lower limb fracture

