Atypical mycobacterial pneumonia

Atypical pneumonia

Auscultation

Avian influenza

Bacterial test positive

Blastomycosis

Bronchopneumopathy

Bronchopulmonary aspergillosis

Burkholderia cepacia complex infection

Burkholderia pseudomallei infection

Burkholderia test positive

COVID-19

COVID-19 pneumonia

Candida pneumonia

Carbon dioxide abnormal

Carbon dioxide increased

Chest X-ray abnormal

Chlamydia test positive

Chlamydial infection

Chronic pulmonary histoplasmosis

Version: 1.0 Date: 01/06/2023

Coccidioidomycosis

Coronavirus infection

Coronavirus pneumonia

Coronavirus test positive

Coxiella test positive

Crepitations

Cryptococcosis

Culture throat positive

PNEUMONIA

Disseminated aspergillosis

Disseminated blastomycosis

Disseminated coccidioidomycosis

Disseminated mucormycosis

Disseminated paracoccidioidomycosis

Disseminated sporotrichosis

Disseminated tuberculosis

Egobronchophony

Embolic pneumonia

Empyema

Enterobacter infection

Enterobacter pneumonia

Enterobacter test positive

Escherichia infection

Escherichia test positive

Francisella test positive

Fungal test positive

H1N1 influenza

H2N2 influenza

H3N2 influenza

Haemophilus infection

Haemophilus test positive

Haemoptysis

Haemorrhagic pneumonia

Hantavirus pulmonary infection

Hantavirus test positive

Herpes simplex pneumonia

Histoplasmosis

Human metapneumovirus test positive

Hypoventilation

Hypoxia

Increased bronchial secretion

Infectious pleural effusion

Influenza

Influenza A virus test positive

Influenza virus test positive

Klebsiella infection

Klebsiella test positive

Legionella infection

Legionella test positive

Low lung compliance

Lower respiratory tract congestion

Lower respiratory tract herpes infection

Lower respiratory tract infection

Lower respiratory tract infection bacterial

Lower respiratory tract infection fungal

Lower respiratory tract infection viral

Lung abscess

Lung consolidation

Lung infiltration

Lung opacity

MERS-CoV test positive

Metapneumovirus infection

Metapneumovirus pneumonia

Middle East respiratory syndrome

Miliary pneumonia

Moraxella infection

Moraxella test positive

Mucormycosis

Mycobacterial infection

Mycobacterium test positive

Mycoplasma infection

Mycoplasma test positive

Nocardiosis

Organising pneumonia

Oxygen saturation abnormal

Oxygen saturation decreased

PCO2 abnormal

PCO2 decreased

PO2 abnormal

PO2 decreased

Paracancerous pneumonia

Paracoccidioides infection

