Parasitic pneumonia

Percussion test abnormal

Pleural effusion

Pleural infection

Pleural infection bacterial

Pleural rub

Pleurisy bacterial

Pleurisy viral

Pleuritic pain

Pneumococcal bacteraemia

Pneumococcal infection

Pneumococcal sepsis

Pneumocystis jirovecii pneumonia

Pneumocystis test positive

Pneumonia

Pneumonia acinetobacter

Pneumonia adenoviral

Pneumonia anthrax

Pneumonia bacterial

Pneumonia bordetella Pneumonia chlamydial

Pneumonia cryptococcal

Pneumonia cytomegaloviral

Pneumonia escherichia

Pneumonia fungal

Pneumonia haemophilus

Pneumonia helminthic

Pneumonia herpes viral

Pneumonia influenzal

Pneumonia klebsiella

Pneumonia legionella

Pneumonia measles

Pneumonia moraxella

Pneumonia mycoplasmal

Pneumonia necrotising

Pneumonia parainfluenzae viral

Pneumonia pneumococcal

Pneumonia proteus

Pneumonia pseudomonal

Pneumonia respiratory syncytial viral

Pneumonia salmonella

Pneumonia serratia

Pneumonia staphylococcal

Pneumonia streptococcal

Pneumonia toxoplasmal

Pneumonia tularaemia

Pneumonia viral Pneumonic plague

Pneumovirus test positive

Post procedural pneumonia

Productive cough

Proteus infection

Proteus test positive

Pseudomonas infection

Pseudomonas test positive

Psittacosis

Pulmonary blastomycosis

Pulmonary congestion

Pulmonary echinococciasis

Pulmonary histoplasmosis

Pulmonary imaging procedure abnormal

Pulmonary mucormycosis

Pulmonary nocardiosis

Pulmonary paracoccidioidomycosis

Pulmonary sepsis

Pulmonary sporotrichosis

Pulmonary syphilis

Pulmonary trichosporonosis

Pulmonary tuberculoma

Pulmonary tuberculosis

Pyopneumothorax

Q fever

Rales

Respiratory tract infection

Respiratory tract infection bacterial

Respiratory tract infection fungal

Respiratory tract infection viral

Rhonchi

SARS-CoV-1 test positive

SARS-CoV-2 antibody test positive

SARS-CoV-2 test false negative

SARS-CoV-2 test positive

Septic pulmonary embolism

Serratia infection

Serratia test positive

Severe acute respiratory syndrome

Sporotrichosis

Sputum abnormal

Sputum culture positive

Sputum discoloured

Sputum purulent

Staphylococcal infection

Staphylococcus test positive

Streptococcal infection

Streptococcus test positive

Suspected COVID-19

Tachypnoea

Tuberculosis

Tuberculous pleurisy

Tularaemia

Use of accessory respiratory muscles

Varicella zoster pneumonia

Venous oxygen saturation abnormal

Venous oxygen saturation decreased

Pneumonia aspiration

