CT 0.7.1	System Organ Class and Preferred Term (Safety Analysis Set)
CT-8.7.1	Incidence of TEAEs of at Least 2% in Any Brex Group and Greater Than Placebo
CT-8.7.2	by MedDRA System Organ Class and Preferred Term (Safety Analysis Set) Incidence of Drug-related TEAEs of at Least 2% in Any Brex Group and Greater
C1-6.7.2	Than Placebo by MedDRA System Organ Class and Preferred Term (Safety
	Analysis Set)
CT-8.8.1	Incidence of TEAEs by MedDRA System Organ Class, Preferred Term and Time to
0.0	First Onset (Safety Analysis Set)
CT-8.8.2	Incidence of Drug-related TEAEs by MedDRA System Organ Class, Preferred Term
	and Time to First Onset (Safety Analysis Set)
CT-8.9.1	Incidence of TEAEs for EPS (Safety Analysis Set)
CT-8.9.2	Incidence of TEAEs for Accidents and Injuries Including Fall (Safety Analysis Set)
CT-8.9.3	Incidence of TEAEs for Cerebrovascular Events (Safety Analysis Set)
CT-8.9.4	Incidence of TEAEs for Cardiovascular Events (Safety Analysis Set)
	· · · · · · · · · · · · · · · · · · ·

CT-8.9.5	Incidence of TEAEs for Effect on Glucose (Safety Analysis Set)
CT-8.9.6	Incidence of TEAEs for Effect on Lipids (Safety Analysis Set)
CT-8.9.7	Incidence of TEAEs for Effect on Weight (Safety Analysis Set)
CT-8.9.8	Incidence of TEAEs for Haematopoietic/Leukopenia (Safety Analysis Set)
CT-8.9.9	Incidence of TEAEs for Hypersensitivity (Safety Analysis Set)
CT-8.9.10	Incidence of TEAEs for Neuroleptic Malignant Syndrome (Safety Analysis Set)
CT-8.9.11	Incidence of TEAEs for Orthostatic Hypotension, Dizziness, and Syncope (Safety Analysis Set)
CT-8.9.12	Incidence of TEAEs for Effect on Prolactin (Safety Analysis Set)
CT-8.9.13	Incidence of TEAEs for QT Prolongation (Safety Analysis Set)
CT-8.9.14	Incidence of TEAEs for Rhabdomyolysis and CPK Elevation (Safety Analysis Set)
CT-8.9.15	Incidence of TEAEs for Seizures (Safety Analysis Set)
CT-8.9.16	Incidence of TEAEs for Somnolence (Safety Analysis Set)
CT-8.9.17	Incidence of TEAEs for Suicidality (Safety Analysis Set)
CT-8.9.18	Incidence of TEAEs for VTE (Thrombotic and Embolic Events) (Safety Analysis Set)
CT-8.9.19	Incidence of TEAEs for Pneumonia (Safety Analysis Set)
CT-8.10.1	Incidence of TEAEs by MedDRA System Organ Class and Preferred Term by Medical Care Category (Safety Analysis Set)
CT-8.10.2	Incidence of TEAEs by MedDRA System Organ Class and Preferred Term by Prior Antipsychotics (Safety Analysis Set)

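### The Pneumonia adverse-event category counts COVID-19, influenza and other infections without pneumonia, and no count of subjects limited to pneumonia is planned beside it

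*SAP*

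**What the plan says.** SAP 9.2.1 names pneumonia-related events as one of 19 categories of interest and refers to Appendix 4 for the definition of each. The planned summary is descriptive: "Numbers and proportions of subjects with the following AEs of interest will be summarized by SOC and PT for each treatment" group and for the pooled brexpiprazole group. The table is CT-8.9.19 and the matching subject listing is CT-9.4.19 (SAP Appendix 5).

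The Pneumonia list in SAP Appendix 4 contains several kinds of term:

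- **Pneumonia terms**, in the dozens, among them COVID-19 pneumonia, Coronavirus pneumonia, Pneumonia influenzal and Pneumonia aspiration.
- **Seven COVID-19 or general coronavirus terms without pneumonia:** COVID-19, Suspected COVID-19, Coronavirus infection, Coronavirus test positive, SARS-CoV-2 test positive, SARS-CoV-2 test false negative and "SARS-CoV-2 antibody test positive".
- **Seven influenza terms without pneumonia:** Influenza, Avian influenza, the H1N1, H2N2 and H3N2 strains, Influenza virus test positive and "Influenza A virus test positive".
- **Other non-pneumonia terms**, such as Escherichia infection, Staphylococcal infection, Bacterial test positive and Productive cough.

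Events that may precede aspiration pneumonia sit in other lists: Dysphagia under neuroleptic malignant syndrome, Choking under hypersensitivity, and "Foreign body aspiration" under accidents and injuries.

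Protocol 2.1 describes "criteria to exclude patients at high risk of cerebrovascular disorder, cardiac disorder, pneumonia, and other infections, which were the causes of death" with atypical antipsychotics, and names those exclusion criteria and the IDMC as the protective measures. The Protocol Synopsis plans the trial from August 2018 to June 2023. SAP 9.2.2 splits all treatment-emergent events at 07 Apr 2020 to show the impact of the pandemic; the categories of interest are not split.

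**The concern.** Pneumonia is a risk that the protocol itself names for this drug class, so a reader of the study report will want to know how many subjects in each arm had it. The planned tables do not answer that. The preferred-term rows separate Pneumonia, Pneumonia bacterial, Pneumonia aspiration and so on, but one subject can have several terms, so the rows cannot be added. The category total counts each subject once, but it also counts a subject with influenza or COVID-19 and no pneumonia. The figure most likely to be quoted as the pneumonia result is therefore a count of respiratory and other infections, in a trial whose planned period spans the pandemic.

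**Working it through.** **Inputs.** The documents give no rate for pneumonia, COVID-19 or influenza, so every rate below is an assumption. Arm sizes are 148 (2 mg), 111 (1 mg) and 148 (placebo), from Protocol 6.1. The only design figure in the documents is power for the primary endpoint. It reproduces: 5.35 / (15.06 × √(1/148 + 1/148)) = 3.06 and 5.35 / (15.06 × √(1/111 + 1/148)) = 2.83, and the noncentral t distribution then gives 86.13% and 80.47% against the stated 86.1% and 80.5%. It has no bearing on this table.

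**Calendar overlap.** Taking 1 Aug 2018 to 30 Jun 2023 as the planned period, 1,179 of 1,794 days (65.7%) follow 07 Apr 2020. This is a share of calendar time, not of subjects or exposure.

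**Effect on the category total.** Let p be the pneumonia rate in an arm and q the rate of listed background infection without pneumonia, equal in both arms and independent of p. The category rate is 1 − (1 − p)(1 − q). The absolute difference is then (p₁ − p₀)(1 − q), so it shrinks only by the factor 1 − q, while the ratio moves towards 1.

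With p = 4% on brexpiprazole and 2% on placebo:

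| q | Placebo | Brexpiprazole | Difference (points) | Ratio |
|---|---|---|---|---|
| 0 | 2.00% | 4.00% | 2.00 | 2.00 |
| 2% | 3.96% | 5.92% | 1.96 | 1.49 |
| 5% | 6.90% | 8.80% | 1.90 | 1.28 |
| 8% | 9.84% | 11.68% | 1.84 | 1.19 |

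**Signal against noise.** No test is planned on this table; power is used here only as a gauge. For 148 v 148 subjects and p = 6% v 2%:

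| q | Difference (points) | Ratio | Power, normal approximation | Power, Fisher exact |
|---|---|---|---|---|
| 0 | 4.0 | 3.00 | 42% | 30% |
| 2% | 3.9 | 1.99 | 30% | 21% |
| 5% | 3.8 | 1.55 | 21% | 16% |
| 10% | 3.6 | 1.31 | 15% | 11% |

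For 4% v 1% and 8% v 2%, the ratio is 4.00 at q = 0 and falls to 1.25 and 1.46 at q = 10%. Normal-approximation power falls from 38% to 11% and from 66% to 26%.

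**Chance imbalance.** Equal q is an expectation, not a guarantee. At q = 5%, about 148 × 0.05 = 7.4 subjects per arm are expected. The standard error of the difference in background infection, assuming independent cases, is √(2 × 0.05 × 0.95 / 148) = 2.5 points. That exceeds the 2-point pneumonia difference in the first table and can act in either direction.

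**What is not affected.** The rows for COVID-19, COVID-19 pneumonia, Influenza, Pneumonia and Pneumonia aspiration do not change with q.

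**The case against.** The strongest reply is that nothing is hidden. CT-8.9.19 is by preferred term, all treatment-emergent events are tabulated the same way (CT-8.2.1) and again by pandemic period (CT-8.10.9), and every case is listed (CT-9.4.19). This stands for individual terms. It does not supply a count of subjects with any pneumonia term, because overlapping rows cannot be summed.

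Secondly, the list is plainly meant as a wide screen, as are others in SAP Appendix 4 (the neuroleptic malignant syndrome list includes Fatigue and Pyrexia), and Protocol 2.1 speaks of pneumonia together with other infections. This also stands. It is a reason to keep the list and add to it. Moving out only the viral terms would still leave Escherichia infection, Staphylococcal infection and similar terms in the total, and would lose any pneumonia coded simply as COVID-19 or Influenza.

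Thirdly, incidental positive tests should rarely enter. The protocol's laboratory table contains no SARS-CoV-2 test, and Protocol 5.1 makes a laboratory result an adverse event only if it is judged medically relevant, leads to discontinuation or meets the criteria for a serious event. That weakens the antibody-test example. It does not touch the diagnoses COVID-19 and Influenza.

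Stronger readings are tempting but not supported:

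- A reader might infer that outbreaks erase a difference between arms. On the planned scale of numbers and proportions the difference hardly moves; the ratio and the precision suffer.
- A reader might infer that CT-8.9.19 was set up to monitor a known cause of death. Protocol 2.1 ties that risk to the exclusion criteria and the IDMC and does not mention this table.
- A reader might infer that filing Choking and Dysphagia elsewhere hides aspiration pneumonia. Pneumonia aspiration is in the Pneumonia list, and choking appears under its own preferred term; only a grouping of possible precursor events is missing.

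**Conclusion.** The point holds in a limited form. The Pneumonia category total in CT-8.9.19 is not an estimate of pneumonia incidence, and no other planned figure counts each subject once across the pneumonia terms. That part rests on the term lists alone, with the assumption that the table carries a category total, as SAP 9.2.1 implies.

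The numerical effect is illustrative. Under equal, independent background infection of 2% to 8%, an assumed ratio of 2.0 becomes 1.49 to 1.19, and the difference goes from 2.00 to between 1.96 and 1.84 points. A chance imbalance in background infection could instead create or mask a difference. How much COVID-19 or influenza would enter is unknown, because the documents give neither rates nor an enrolment curve.

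No efficacy result, formal safety test or stopping decision is affected. This is an inexpensive improvement to the reporting of a risk that the protocol names.

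**What to change.** Keep the Appendix 4 list and the existing category total. Before unblinding, so that the choice of terms is blind to results, add to CT-8.9.19 for each arm and for pooled brexpiprazole:

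1. A row counting each subject once with any pneumonia preferred term, including COVID-19 pneumonia, Coronavirus pneumonia, Pneumonia influenzal and Pneumonia aspiration. List the chosen terms in Appendix 4.
2. A separate row for the COVID-19/coronavirus and influenza terms without pneumonia.

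Optionally, add a grouped row for Dysphagia, Choking, Foreign body aspiration and Pneumonia aspiration, leaving those terms in their present categories as well.

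The cost is a short SAP appendix edit and a few more descriptive rows from data already coded. The narrow row may miss pneumonia coded only as COVID-19 or Influenza; the unchanged broad total still captures those subjects.
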